A population pharmacokinetic approach will be implemented using sparse sampling collection. Collection of plasma samples for phenobarbital analysis will be obtained after each loading dose and will follow the sampling guidelines in the schedule of activities (Section 1.3). Additional plasma samples will be obtained at the completion of the treatment period or at early study discontinuation. In order to maintain the study blind, the phenobarbital plasma concentrations will not be made available to the study personnel.

Seizure management in the treatment period will be determined by cvEEG monitoring. Recording of all vital signs and collection of laboratory safety monitoring and collection of phenobarbital plasma samples will be dependent on the clinical management and status of the neonate. The principal investigator will be allowed to discontinue the neonate from the study protocol at any time throughout the study protocol and allowed to administer alternative anticonvulsant therapy as medically required or following standard of care guidelines.

The study treatment period for the primary study analysis will end 24 hours after the neonate meets the seizure criteria and receives the initial phenobarbital study dose (i.e. T0-24 hr). Prior to completing the Treatment Period or early study discontinuation, cvEEG assessment, clinical seizure assessment, and vital signs will be recorded, clinical laboratory tests will be performed, and a phenobarbital plasma sample will be collected. The neonate will be monitored for an additional 24 hours (Follow-up Period) after the Treatment Period is completed. During the 24-hour Follow-up Period general seizure activity, administration of additional non-study anticonvulsant medication, and adverse events will be recorded. Neonates requiring ongoing/maintenance intravenous phenobarbital therapy following study treatment completion will enter an Open Label Extension Period (up to 3 days) and will be monitored for safety and additional phenobarbital plasma samples will be obtained while they are on therapy and until hospital discharge. All study related assessments and work related to the study will be compensated by the funding Sponsor.

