7.1 Discontinuation of Study Drug

Discontinuation from intravenous phenobarbital does not mean discontinuation from the study, and remaining study procedures should be completed as indicated by the study protocol. If a clinically significant finding is identified (including, but not limited to changes from baseline) after enrollment, the investigator or qualified designee will determine if any change in participant management is needed.

The data to be collected at the time of study drug discontinuation will include the following:

- Vital Signs
- Collection and review of Laboratory Tests (Hematology, Chemistry and Coagulation)
- cvEEG Assessment
- Clinical Seizure Assessment
- Phenobarbital PK Samples
- Recording of Additional Anticonvulsant Medication
- Concomitant Medication Review
- Adverse Events Evaluation

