7.2 Participant Discontinuation/Withdrawal from the Study

Parents/Legal Guardians are free to withdraw their study participants in the study at any time upon request.

An investigator may discontinue or withdraw a study participant from the study for the following reasons:

- If any clinical adverse event (AE), laboratory abnormality, or other medical condition or situation occurs such that continued participation in the study would not be in the best interest of the study participant
- If the participant meets an exclusion criterion (either newly developed or not previously recognized) that precludes further study participation
- Participant unable to receive study drug

The reason for study participant discontinuation or withdrawal from the study will be recorded on the Study Participant Disposition Case Report Form (CRF). Study participants who sign the informed consent form and are randomized but do not receive the study drug may be replaced. Study participants whose parent/legal guardian sign the informed consent form, and are randomized and receive the study drug, and subsequently withdraw, or are withdrawn or discontinued from the study, will not be replaced.

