7.4.1 Stopping rules for study participants

7.4.1.1 *Efficacy*

Study participants will not be stopped in the trial if seizure cessation is not achieved with one or two doses of phenobarbital. Study participants will be placed on second-line treatments per institutional protocol/standard operating procedures and will continue to be observed. Sponsor is not providing sites with second-line anticonvulsant treatments.

7.4.1.2 *Safety*

Newborns who will be enrolled in this study are at high risk for several serious medical complications and death related to underlying etiology of their seizures. It is very unlikely that phenobarbital will result in death or any serious adverse event. The following adverse events not described in the investigator brochure for phenobarbital will be considered expected adverse events in this population:

- Clinical or electrographic seizures
- Multiorgan Failure
- Abnormal lab values associated with organ failure
- Death
- Any other adverse events associated with systemic asphyxia and hypoxic-ischemic encephalopathy in newborns

Any adverse events that are expected, not related to phenobarbital, and not severe in nature will be recorded in the database and reviewed at regular meetings of the DSMB. The DSMB will be able to review significant trends of adverse events at their meetings, since the DSMB will be the only party not blinded in this trial. After review of the data, the DSMB will report to NEMA regarding the risks of the study and whether the risks are consistent with what is described in the informed consent form. These reports will be provided by NEMA to the local IRBs for determining continuing review, and to the FDA for annual IND safety reports.

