9.4.2 Analysis of the Primary Efficacy Endpoint(s)

The primary endpoint will be summarized by number and percent of participants with events and compared by a log binomial model (a generalized linear model [GLM]) that includes treatment as a study variable, which will generate risk ratio (RR) together with their 95% CIs of having a primary outcome between high dose and low dose groups. A study participant who is withdrawn from the study within the first 24 hours after treatment will be considered not to have achieved the primary endpoint. Treatment of such dropouts with respect to other endpoints will be specified in the SAP.

In addition, covariate adjustment will be performed by GLM model with treatment as a study variable and, gender, gestational age, birth weight, apgar scores, liver function tests, seizure etiology, therapeutic hypothermia and pre-treatment seizure burden as covariates. From this

model, adjusted RR together with their 95% confidence interval will be derived. Imputation for these baseline missing covariates will be carried out for adjusted analysis.

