3.7.2. Secondary outcomes

Efficacy

- Percent of neonates who do not require additional seizure treatment after 2 hours of the first dose of phenobarbital.

CONFIDENTIAL

- Percent of neonates who do not require additional seizure treatment after the second dose of phenobarbital within the first 24 hours of treatment.
- Seizure burden over 24 hours following initial administration of the phenobarbital injection.
- Seizure burden over 48 hours following initial administration of the phenobarbital injection.
- Percent of neonates requiring alternative anticonvulsive therapy for the management of seizures at 24 and 48 hours.
- Time period between the first dose and second dose of intravenous phenobarbital in neonates randomized.
- Time period between the second dose of intravenous phenobarbital and alternative anticonvulsant treatment in neonates
- Time period between the first dose of intravenous phenobarbital and administration of an alternative anticonvulsant treatment in neonates randomized.

Safety

The following safety assessments will be performed during the study:

- Type, incidence, and severity of adverse events
- Physical examination
- Vital signs (blood pressure [arterial line], respiration rate, pulse rate, oxygen saturation and temperature)
- Clinical laboratory tests (hematology, serum chemistry)

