5.5.3. Other Outcomes (e.g. Safety, secondary outcomes etc.)

No imputation will be performed

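### Neonates taken off study around a switch to another anticonvulsant can be missing from the 24- and 48-hour secondary endpoints, and the SAP has no rule for them

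*Protocol*

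**What the plan says.** **Leaving and staying.** Under Protocol 4.1 the principal investigator is "allowed to discontinue the neonate from the study protocol at any time throughout the study protocol and allowed to administer alternative anticonvulsant therapy", where medically required or under standard-of-care guidelines. Protocol 7.4.1.1 says: "Study participants will not be stopped in the trial if seizure cessation is not achieved with one or two doses of phenobarbital". It adds: "Study participants will be placed on second-line treatments per institutional protocol/standard operating procedures and will continue to be observed". Protocol 7.1, on stopping study drug, says: "Discontinuation from intravenous phenobarbital does not mean discontinuation from the study, and remaining study procedures should be completed as indicated by the study protocol". Protocol 7.2 lists reasons for withdrawal from the study, one of which is "Participant unable to receive study drug".

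**Endpoints.** SAP 3.7.2 includes "Percent of neonates requiring alternative anticonvulsive therapy for the management of seizures at 24 and 48 hours", and seizure burden over 24 and over 48 hours.

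**Missing data.** For the primary endpoint, withdrawal within 24 hours (Protocol 9.4.2) or a missing response (SAP 5.5.2) counts as failure. For the rest, Protocol 9.4.2 says: "Treatment of such dropouts with respect to other endpoints will be specified in the SAP". SAP 5.5.3 answers: "No imputation will be performed". SAP 5.2 bases percentages on subjects with data, unless noted otherwise.

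**The concern.** One clinical course, a neonate who is not controlled and moves to another drug, can be handled in two ways. A site relying on 7.4.1.1 keeps the neonate under observation. A site relying on 4.1 may discontinue the neonate from the study protocol. The primary analysis deals with both. The secondary analyses do not: the second neonate may contribute no value, or a truncated one, to the endpoints that describe what happens after phenobarbital fails.

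Such loss would be related to the outcome. An analysis of available data does not correct for that, and neither does the GEE that SAP 7.2.1 plans for repeated binary outcomes. At stake are the estimates of need for alternative therapy and of seizure burden, and their consistency with the primary result.

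**Working it through.** **1. The plan's own figures.** The documents give no rate for alternative therapy. The sample size serves only to fix the number per arm. Inputs (Protocol 9.1 and 9.2, SAP 3.6): control in 50% and 70%, two-sided alpha 0.05, power 80%, 1:1 allocation, 5% dropout.

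n per arm = [1.960·√(2·0.6·0.4) + 0.842·√(0.5·0.5 + 0.7·0.3)]² / 0.2² = 93, total 186. Then 186/0.95 = 195.8, so 196 randomized, or 98 per arm. The plan's figures reproduce.

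**2. When is a record required?**

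- *Drug given before or at discontinuation.* Second-line therapy is recorded as a concomitant medication (4.1). The seizure prompting each further drug is documented (8.1.4). Anticonvulsant use is in the data collected when study drug is stopped (7.1) and in the Follow-up/Early Discontinuation list (4.1.4). The event is observed. It could be lost only if the endpoint is read as status at 24 or 48 hours and not as use by then.
- *Drug given after the neonate has left the study protocol.* No section requires a record. The neonate is missing, or is carried as having had no alternative therapy; the SAP does not say which.
- *Seizure burden.* Section 8.2.8 runs cvEEG to 48 hours for participants in general, but no section extends this to a neonate discontinued from the study protocol. Burden can be missing or cover a shorter time.

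**3. What loss could do.** Assumption, not in the documents: half of the planned first-dose failures (50% low, 30% high) receive alternative therapy by 24 hours, so p = 25% (low) and 15% (high). The true difference, high minus low, is −10.0 points. Let f be the share of event neonates with no record; f is also assumed. If they leave the denominator, the observed rate is p(1 − f)/(1 − pf).

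| f low | f high | Low | High | Difference (points) |
|---|---|---|---|---|
| 0 | 0 | 25.0% | 15.0% | −10.0 |
| 0.25 | 0.25 | 20.0% | 11.7% | −8.3 |
| 0.50 | 0.50 | 14.3% | 8.1% | −6.2 |
| 0.25 | 0.10 | 20.0% | 13.7% | −6.3 |
| 0.10 | 0.25 | 23.1% | 11.7% | −11.4 |

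If they stay in the denominator as non-events, equal loss gives −10.0·(1 − f), which is −7.5 at f = 0.25 and −5.0 at f = 0.50.

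**4. Against the planned dropout.** With equal f, the number lost is 98·(0.25 + 0.15)·f: 9.8 neonates at f = 0.25 and 19.6 at f = 0.50. Planned dropout of every kind is about 10 (5% of 196). The first scenario uses all of it and the second twice as much.

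As an extreme case, suppose all 10 dropouts are event neonates, with 24/98 (low) and 15/98 (high) true events, a difference of −9.2 points:

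- all 10 lost from low dose: 14/88 vs 15/98, difference −0.6;
- all 10 lost from high dose: 24/98 vs 5/88, difference −18.8;
- 5 lost from each: 19/93 vs 10/93, difference −9.7.

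**The case against.** The strongest reply is that the protocol requires the event to be recorded when it happens. A neonate given another drug and then taken off study has an observed event. A no-imputation rule does not delete it, and the neonate counts as having data. This stands. A reader might infer that the endpoint systematically loses the neonates who had the event; the recording requirements in 4.1, 4.1.4, 7.1 and 8.1.4 do not support that. What remains is a drug given after leaving, a reading of the endpoint as status at a time point, and the burden endpoints.

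Two apparent contradictions are also weaker than they look. Section 7.1 concerns stopping study drug, whereas 4.1 concerns leaving the study protocol. The real tension is between 4.1 and 7.4.1.1. The inability-to-dose reason in 7.2 most naturally means neonates who were never dosed, since that section goes on to allow replacement of those randomized but untreated. It is not shown to cover a switch after dosing, but nothing limits it either.

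Finally, SAP 5.6 treats secondary analyses as exploratory, and the loss fractions are assumed. Both are true. They limit the consequence, but they do not supply the rule that Protocol 9.4.2 promised.

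**Conclusion.** The gap is real and limited. Protocol 4.1 and 7.4.1.1, with 7.2, leave it open whether a neonate who switches stays under observation. No section requires data to 48 hours after leaving, and the SAP gives one general line where a dropout rule was due. A neonate taken off study around a switch within 24 hours can therefore be a primary failure and yet be absent from the alternative-therapy endpoint, with burden missing or shortened.

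The size is unknown. If all of the planned dropout were event neonates, lost in proportion to events, the assumed 10.0-point difference would become 8.3. A reader might infer that need is understated more in the arm with more failures, so that the difference always shrinks. That holds only under assumptions such as equal loss fractions; under unequal loss the difference ran from −0.6 to −18.8 around a true −9.2. All of this rests on assumed event rates and loss fractions.

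The primary endpoint and the sample size are unaffected. The change should be made, but it is not critical to the trial's main conclusion.

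**What to change.** 1. The sponsor should reconcile Protocol 4.1, 7.2 and 7.4.1.1 on whether a neonate who switches remains in the study. No view is taken here on which rule should govern, and clinical discretion need not change.
2. Separate two statuses in the protocol and CRF: switched or stopped study drug, and withdrawn from data collection. For the first, continue recording anticonvulsant use, and whatever cvEEG data are available, to T0+48 hours unless consent is withdrawn.
3. In SAP 3.7.2, define the alternative-therapy endpoint as cumulative use by 24 hours and by 48 hours.
4. In SAP 5.5.3, count a neonate discontinued within the window in order to receive, or after receiving, an alternative anticonvulsant as an event. Add a sensitivity analysis that counts neonates who leave without a record as events.

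The cost is some protocol and SAP wording and slightly more data entry for neonates who switch. The SAP text should be settled before unblinding.

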4.1.1 Definitions

4.1.2 Screening Period

Parental/Legal Guardian consent must be provided prior to study participant enrollment and prior to any study-related procedures being done. All screening evaluations must be completed before the study participant enters the Treatment Period. Screening Period is from time of consent or start of cvEEG (which ever comes last) and up to 24 hours (T(-)24-0 hrs).

The following procedures will be completed during the Screening Period (prior to dosing):

- Informed Consent
- NICU Admission

- Review of Inclusion/Exclusion Criteria
- Delivery History
- Medical History (includes Family History of Seizures and Delivery Complications)
- Physical Examination (including neurologic exam)
- Vital Signs (baseline assessment)
- Height/Length
- Head Circumference
- Abdominal Circumference
- Apgar Score
- Body Weight
- Collection and review of Laboratory Safety Tests (Hematology, Chemistry and Coagulation) (baseline assessment)
- cvEEG recording and monitoring
- Prior and Concomitant Medication Review
- Adverse Events Evaluation

Gestational age can be calculated using either ultrasound, last menstrual period, or neonatal assessment.

4.1.3 Treatment Period

Treatment Period is from time of first drug administration and up to 24 hours (T0-24 hrs).

The following procedures will be performed during the Treatment Period:

- Review of Inclusion/Exclusion Criteria
- Vital Signs
- Collection and review of Laboratory Tests (Hematology, Chemistry and Coagulation)
- Randomization
- cvEEG recording and monitoring
- Clinical Seizure Assessment
- Initial Phenobarbital Administration
- Additional Phenobarbital Administration
- Phenobarbital Plasma Samples
- Recording of Additional Anticonvulsant Medication
- Concomitant Medication Review
- Adverse Events Evaluation

4.1.4 24 Hour Follow-Up Period /Early Discontinuation/End of Study

Follow-Up Period is from end of Treatment Period and up to 24 hours (T24-48 hrs).

The following procedures will be performed during the Follow-up Period:

- Physical Examination (including neurologic examination)
- Vital Signs
- Collection and review of Laboratory Tests (Hematology, Chemistry and Coagulation)
- cvEEG recording and monitoring
- Clinical Seizure Assessment
- Phenobarbital Plasma Samples
- Recording of Additional non-study Anticonvulsant Medication
- Concomitant Medication Review
- Adverse Events Evaluation

4.1.5 Open-Label Extension Period

Open-Label Extension Period is from start of first phenobarbital maintenance dose and up to 72 hours. Maintenance cannot be started <24 hours after T0 (e.g., not during Treatment Period). If it is determined that maintenance phenobarbital is no longer needed, study participant will be discontinued from the Open-Label Extension Period and final study assessments will be completed based on schedule of activities (Section 1.3).

The following procedures will be performed during the Open-Label Extension Period:

- Vital Signs
- Physical Examination (including neurologic examination)
- Collection and review of Laboratory Tests (Hematology, Chemistry and Coagulation)
- Clinical Seizure Assessment
- Phenobarbital Administration
- Phenobarbital Plasma Samples every 24 hours
- Recording of Additional Anticonvulsant Medication
- Concomitant Medication Review
- Adverse Events Evaluation

4.2 Scientific Rationale for Study Design

4.3 Justification for Dose

The clinical management of neonatal seizures and the doses (both partial and cumulative) of phenobarbital administered as first line therapy have generally varied among clinicians and institutions. A total daily dose up to 50 mg/kg have been recommended for the treatment of neonatal seizures (12). Based on the published literature and current standard practices, the most frequently used initial doses of phenobarbital to treat neonatal HIE are 20 to 30 mg/kg i.v. followed by maintenance dose of 4 to 6 mg/kg per day (2). If seizures do not resolve with the initial dose, repeat boluses of 10 to 20 mg/kg may be administered with a goal of approximately 50 µg/mL phenobarbital serum level or a total 24 hour total dose of 50 mg/kg (2).

The Sponsor proposes evaluating two double-blind intravenous dose regimens of phenobarbital: Phenobarbital 20 mg/kg (initial dose) followed by 20 mg/kg (second dose, if required) [total daily dose 40 mg/kg] or phenobarbital 40 mg/kg (initial dose) followed by 10 mg/kg (second dose, if required)[total daily dose of 50 mg/kg].

If seizures do not resolve following the initial or second dose of phenobarbital, the PI or site designee will choose an alternate drug for additional dosing. The PI or site designee will be permitted to choose an alternate drug of choice if the neonate does not achieve appropriate seizure control at any time during the study.

For ethical concerns, there will not be a placebo control group.

4.4 End of Study Definition

A study participant is considered to have completed the study if he or she has completed all phases of the study including the last scheduled procedure prior to discharge shown in the Schedule of Activities (SoA).

The end of the study is defined as completion of the last procedure shown in the SoA in the trial for the last enrolled study participant.

5 Study Population

5.1 Inclusion Criteria

In order to be eligible to participate in this study, an individual must meet all of the following criteria:

1. Male or female neonates with a gestational age of ≥ 34 - ≤ 44 weeks admitted into the NICU with a high probability of developing seizures (e.g., HIE, stroke, intracerebral hemorrhage, central nervous system infection)
2. Parental/Legal Guardian informed consent (in-person or remote consent)
3. Undergoing continuous video electroencephalogram (cvEEG) monitoring
4. Has evidence of electrographic seizure burden of at least 30 seconds/h

5.2 Exclusion Criteria

An individual who meets any of the following criteria will be excluded from participation in this study:

1. Received anticonvulsant treatment, including phenobarbital, prior to randomization (with exception of lorazepam and midazolam administered ≥ 8 hours before enrollment)
2. Strong suspicion or confirmed diagnosis of brain malformation, inborn error of metabolism genetic syndrome, or major congenital malformation prior to randomization

3. Seizures responding to correction of hypoglycemia, hypocalcemia or any other metabolic disorder
4. Death appears to be imminent as assessed by the NICU attending physician
5. Is currently enrolled in another study assessing the same and/or similar primary/secondary endpoints with/without drug treatment.

Study participants who may be already participating in another neonatal clinical trial (e.g., registry or observational) that meet all MI-5780 inclusion criteria and none of the MI-5780 exclusion criteria as well as can meet study assessment requirements, can be enrolled into this study. In addition, study participants enrolled in this trial can enroll in other neonatal trials as long as 1) the inclusion criteria for study MI-5780 continue to be met 2) none of the exclusion criteria for study MI-5780 are met 3) the other study will not result in minor or major MI-5780 protocol deviations.

